## 7. STUDY PROCEDURES

The schedule of assessments to be conducted in the study is provided in tabular form in [Appendix 1](#).

### 7.1. Subject Enrollment and Treatment Assignment

Following provision of informed consent and completion of all Screening and Day 1 predose assessments, if a subject meets all protocol eligibility requirements the Investigator or designee will randomize the subject using the IRT system described in [Section 6.1.1](#). Protocol waivers will not be granted.

#### 7.1.1. Screen Failures

Screen failures are defined as subjects who consent to participate in the clinical study but are not subsequently randomized to study treatment. Minimal information should be retained on all screen failures including demography, screen failure details, eligibility criteria, and any serious adverse event (SAE) information.

Individuals who do not meet the protocol eligibility criteria for participation in this study (ie, screen failures) may not be rescreened; however, retest for some laboratory parameter(s) is permitted if there is considered to be a specific issue related to the collection, shipping, processing, or analysis of a sample (eg, receipt of a hemolyzed sample at the testing laboratory, or samples received by the testing laboratory outside of the acceptable temperature range). Subjects who meet all study eligibility requirements but are not able to complete the Day 1 visit within the prespecified 45-day window may be rescreened for the study.

### 7.2. Screening Assessments (Day -45 to Day -1)

It is recommended, though not mandated, that invasive procedures, such as a liver biopsy (if required) are not conducted until it has been determined that the subject is broadly eligible for study participation.

The following Screening assessments must be completed within 45 days of the scheduled Day 1 visit:

- Obtain written informed consent
- Record demographics and medical history, including HBV history and HBV treatment history
- Liver staging (as required per inclusion criteria, ie, fasting FibroScan)
- Measure height and body weight
- Vital signs (temperature, heart rate, respiration rate, and blood pressure)

- Complete physical examination (excluding breast and genitalia, unless indicated)
- 12-lead ECG
- Review of concomitant medications
- Review of AEs occurring after provision of informed consent
- Laboratory analyses (additional details are provided in the Laboratory Manual):
  - Safety labs: chemistry, hematology, coagulation, serum AFP, follicle-stimulating hormone (FSH) (females only), TSH and T4, serum pregnancy test, urinalysis, urine drug test ([Appendix 2](#))
  - Virology: HBV genotype, HBV DNA, HBsAg, HBeAg, HBsAb, HBeAb, sample for HBV nucleic acids, HIV Ab, HCV Ab, HDV Ab, HAV (IgM), HEV (IgM), HBcAb (IgM; see Inclusion Criterion #5, [Section 5.2](#)) ([Appendix 2](#))
  - HBV sequencing: a blood sample for sequencing of the HBV polymerase coding region will be collected and stored for analysis only in the event of any observed viral breakthrough or blunted response ([Appendix 2](#))

### 7.3. Day 1

The following assessments must be completed predose on Day 1:

- Update medical history, including HBV history and HBV treatment history
- Measure body weight
- Vital signs (temperature, heart rate, respiration rate and blood pressure)
- Complete physical examination (excluding breast and genitalia, unless indicated)
- 12-lead ECG
- Review concomitant medications
- Review AEs
- Confirm subject eligibility
- Complete randomization
- Laboratory analyses (additional details are provided in the Laboratory Manual):
  - Safety labs: chemistry, hematology, coagulation, urine and serum pregnancy tests, urinalysis, urine drug test ([Appendix 2](#))
  - Virology: HBV DNA, HBV pgRNA, HBsAg, HBeAg, HBcAg, HBsAb, HBeAb, sample for HBV sequencing and HBV nucleic acids ([Appendix 2](#))
- PK samples: predose samples for 731, Peg-IFN $\alpha$ , and ETV

Dosing:

- Study drug administration (731, ETV and Peg-IFN $\alpha$  [as applicable])

The following assessments must be completed postdose on Day 1:

- Provide dosing diary to subjects
- Study drug dispensation (731, ETV, and Peg-IFN $\alpha$  [as applicable])
- PK samples: postdose samples for 731, Peg-IFN $\alpha$ , and ETV between 2 and 4 hours following study drug administration ([Section 7.11](#))

#### 7.4. Study Week 1

The following assessments are performed at Study Week 1:

- Symptom-directed physical examination
- Review concomitant medications
- Review AEs
- Laboratory analyses (additional details are provided in the Laboratory Manual):
  - Virology: HBV DNA, HBV pgRNA, sample for HBV sequencing and HBV nucleic acids ([Appendix 2](#))
- Review dosing diary and assess drug accountability

#### 7.5. Study Weeks 2 Through 24

The following assessments are performed at Study Weeks 2, 4, 6, 8, 12, 16, 20, and 24 (inclusive) unless otherwise indicated. Subjects who discontinue treatment before Week 24 should immediately undergo the assessments listed for the Premature Termination Visit and then continue the scheduled follow-up assessments. A visit window of  $\pm 3$  days is applied to each visit through Week 20. A visit window of -3 days is applied to Week 24 ([Appendix 1](#)).

- Liver staging (Week 24 only)
- Measure body weight (Week 24 only)
- Vital signs (temperature, heart rate, respiration rate, and blood pressure; not at Week 6)
- Complete physical examination (excluding breast and genitalia, unless indicated; Week 24 only)
- Symptom-directed physical examination (not at Week 24)
- 12-lead ECG (Weeks 12 and 24 only)
- Review concomitant medications
- Review AEs
- Laboratory analyses (additional details are provided in the Laboratory Manual):
  - Safety labs: chemistry (not at Week 6), hematology (not at Week 6), coagulation (not at Week 2 or 6), TSH (only at Weeks 12 and 24), urinalysis (not at Week 2 or 6), urine pregnancy test (not at Week 6) ([Appendix 2](#))
  - Virology: HBV DNA, HBV pgRNA, HBsAg (not at Week 2 or 6), HBeAg (not at Week 2 or 6), HBcAg (not at Week 2 or 6), HBsAb and HBeAb (Weeks 12 and 24 only), sample for HBV sequencing and HBV nucleic acids ([Appendix 2](#))

- PK samples: samples for 731, Peg-IFN $\alpha$ , and ETV between 30 min and 2 hours postdose at Weeks 2, 8, 12, and 24, and between 4 and 6 hours postdose at Weeks 16 and 20. Predose samples for 731, Peg-IFN $\alpha$ , and ETV will be collected at Week 4 and Week 24 only ([Section 7.11](#))
- Review dosing diary and assess drug accountability
- Study drug dispensation (not at Weeks 2 and 6; Peg-IFN $\alpha$  will not be dispensed at Week 24)
- Study drug administration (731 and ETV in-clinic [except at Weeks 2 and 6]; Peg-IFN $\alpha$  may be administered at home)

## 7.6. Study Weeks 28 Through 48

The following assessments are performed at Study Weeks 28, 32, 36, 40, 44, and 48 (inclusive) unless otherwise indicated. Subjects who discontinue treatment before Week 48 should immediately undergo the assessments listed for the Premature Termination Visit and then continue the scheduled follow-up assessment. A visit window of  $\pm 3$  days is applied to each visit through Week 44. A visit window of -3 days is applied to Week 48 ([Appendix 1](#)).

- Liver staging (Week 48 only)
- Measure body weight (Week 48 only)
- Vital signs (temperature, heart rate, respiration rate, and blood pressure)
- Complete physical examination (excluding breast and genitalia, unless indicated; Week 48 only)
- Symptom-directed physical examination (not at Week 48)
- 12-lead ECG (Week 48 only)
- Review concomitant medications
- Review AEs
- Laboratory analyses (additional details are provided in the Laboratory Manual):
  - Safety labs: chemistry, hematology, coagulation, urinalysis (Week 48 only), urine pregnancy test ([Appendix 2](#))
  - Virology: HBV DNA, HBV pgRNA, HBsAg, HBeAg, HBcAg, HBsAb and HBeAb (Week 48 only), sample for HBV sequencing and HBV nucleic acids ([Appendix 2](#))
- PK samples: samples for ETV may be collected predose at Week 44 ([Section 7.11](#))
- Study drug administration (731 and ETV)
- Review dosing diary and assess drug accountability
- Study drug dispensation (only ETV will be dispensed at Week 48, not 731)

## 7.7. Study Weeks 52 Through 60 (Follow-up Assessments)

All subjects, including those who prematurely discontinue treatment or complete treatment per protocol will enter a 12-week follow-up period. Subjects will remain on ETV during the follow-up period. The following assessments are performed every 4 weeks unless otherwise indicated. A visit window of  $\pm 5$  days is applied from Weeks 52 through 60.

- Measure body weight (Week 60 only)
- Vital signs (temperature, heart rate, respiration rate and blood pressure)
- Complete physical examination (excluding breast and genitalia, unless indicated; Week 60 only)
- Symptom-directed physical examination (not at Week 60)
- 12-lead ECG (Week 60 only)
- Review concomitant medications
- Review AEs
- Laboratory analyses (additional details are provided in the Laboratory Manual):
  - Safety labs: chemistry, hematology, coagulation, urinalysis, urine pregnancy test ([Appendix 2](#))
  - Virology: HBV DNA, HBV pgRNA, HBsAg, HBeAg, HBcAg, HBsAb and HBeAb (Week 60 only), sample for HBV sequencing and HBV nucleic acids ([Appendix 2](#))
- Review dosing diary
- Assess drug accountability (final drug accountability performed at Week 60)
- Study drug dispensation (final study drug dispensation performed at Week 56)
- Study drug administration (ETV)

## 7.8. Unscheduled Visit

An Unscheduled Visit may be performed at any time at the discretion of Investigator in order to further evaluate a subject. The specific assessments to be performed at these visits would be determined by the Investigator according to nature of the subject specific follow-up required, however at a minimum the assessments would include the following:

- Vital signs (temperature, heart rate, respiration rate and blood pressure)
- Symptom-directed physical examination
- Review concomitant medications
- Review AEs
- Laboratory analyses (additional details are provided in the Laboratory Manual):
  - Safety labs: chemistry, hematology, coagulation, urinalysis, urine drug test, urine pregnancy test ([Appendix 2](#))

- Virology: HBV DNA, HBV pgRNA, HBsAg, HBeAg, HBcrAg, sample for HBV sequencing, and HBV nucleic acids ([Appendix 2](#))
- PK samples: samples for 731 and Peg-IFN $\alpha$  (if appropriate), and ETV ([Section 7.11](#))

Assessments performed should be documented in the subject's source documentation. Clinical laboratory assessments should be conducted through the central laboratory. The minimum assessments to be completed when managing ALT elevations at an Unscheduled Visit are noted in [Section 9.4](#).

## 7.9. Premature Termination Visit

Should a subject prematurely discontinue treatment ([Section 7.10.1](#)) or discontinue from the study ([Section 7.10](#)), a Premature Termination Visit should be scheduled. While the Investigator may include additional assessments and evaluations determined by the status of the individual subject, at the minimum, the following assessments should be performed as soon as feasibly possible:

- Measure body weight
- Vital signs (temperature, heart rate, respiration rate, and blood pressure)
- Complete physical examination (excluding breast and genitalia unless indicated)
- 12-lead ECG
- Review concomitant medications
- Review AEs
- Laboratory analyses (additional details are provided in the Laboratory Manual):
  - Safety labs: chemistry, hematology, coagulation, urinalysis, urine drug test, urine pregnancy test ([Appendix 2](#))
  - Virology: HBV DNA, HBV pgRNA, HBsAg, HBeAg, HBcrAg, HBsAb, and HBeAb, sample for HBV sequencing and HBV nucleic acids ([Appendix 2](#))
  - PK samples: samples for 731 and Peg-IFN $\alpha$  (if appropriate), and ETV ([Section 7.11](#))
- Review dosing diary and assess drug accountability (if applicable)

## 7.10. Discontinuation

A subject may withdraw from the study at any time at his/her own request or may be withdrawn at any time at the discretion of the Investigator or Sponsor for safety, behavioral, compliance, or administrative reasons. This is expected to be uncommon. At the time of discontinuation from the study, a Premature Termination Visit should be conducted ([Section 7.9](#)). If the subject withdraws consent for disclosure of future information, the Sponsor may retain and continue to use any data collected before such withdrawal of consent. If a subject withdraws from the study, he/she may request destruction of any samples taken and not tested, and the Investigator must document this in the site study records.

### **7.10.1. Discontinuation from Treatment**

If an individual subject is, in the judgement of the Investigator, not satisfactorily tolerating study drug treatment due to AEs, then – in consultation with the Sponsor – the subject may discontinue treatment with 731 or Peg-IFN $\alpha$  (if applicable). Entecavir may be continued at the discretion of the Investigator. Subjects who prematurely discontinue treatment (731 or Peg-IFN $\alpha$  as applicable) should immediately undergo the assessments listed for the Premature Termination Visit ([Section 7.9](#)) and then continue scheduled follow-up assessments ([Section 7.7](#)).

In this study, subjects will be closely monitored for ALT elevations and declining hepatic function. Procedures to be followed for these subjects are described in [Section 9.4](#). Study treatment (731 or Peg-IFN $\alpha$  as applicable) will be discontinued in subjects with confirmed evidence of declining hepatic function during treatment, a Premature Termination Visit ([Section 7.9](#)) will be completed, and subjects will subsequently undergo the follow-up assessments described in [Section 7.7](#). Entecavir may be continued at the discretion of the Investigator in accordance with local practice.

Any female subject with a negative urine pregnancy test at Baseline (Day 1) who is subsequently found to be positive on the Baseline (Day 1) serum pregnancy test should immediately discontinue treatment with 731 and Peg-IFN $\alpha$ , as applicable. At future visits, any positive urine pregnancy test will require confirmation by a serum pregnancy test. Female subjects with a positive serum pregnancy test should immediately discontinue treatment with 731 and Peg-IFN $\alpha$ , as applicable. In these instances, entecavir may be continued at the discretion of the Investigator in accordance with local practice and the approved ETV package insert. These subjects may be replaced at the discretion of the Sponsor.

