## **4. STUDY PLAN**

### **4.1. Study Design**

[figure not shown]
This is a randomized Phase 2a, multicenter, open-label study evaluating the safety, antiviral activity, and PK of 731 administered in addition to ETV with or without Peg-IFN $\alpha$  in treatment-naïve, Chinese subjects with CHB. The study will be conducted at approximately 5 to 10 study sites in China.

Approximately 60 eligible subjects with HBeAg positive CHB will be randomly assigned in a 1:1:1 ratio to the treatment groups shown in the study overview presented in [Figure 1](#).

Treatment with 731 and/or ETV will be administered orally, once daily; treatment with Peg-IFN $\alpha$  will be administered subcutaneously, once weekly. Group 1 will receive 731+ETV for 24 weeks, Group 2 will receive 731+ETV+Peg-IFN $\alpha$  for 24 weeks. Group 3 will receive ETV+Peg-IFN $\alpha$  for 24 weeks. All subjects will receive 731+ETV from Week 24 through Week 48 and then ETV alone from Week 48 through Week 60 during the 12-week follow-up period.

Treatment assignments will be stratified by the HBV genotype (GT; ie, GT A or B vs GT C or D, vs other GTs) and baseline ALT (ie, ALT  $<5 \times$  upper limit of normal [ULN] vs ALT  $\geq 5 \times$  ULN) during the Screening visits.

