Study drug accountability				X	X	X	X	X	X	X	X	X 	X	X 	X 	X	X	
Study drug dispensation 			X			X		X	X	X	X	X	X	X	X 			
In-clinic dosing 731 			X			X		X	X	X	X	X	X	X 				
In-clinic ETV dosing 			X			X		X	X	X	X	X	X	X	X 			
In-clinic Peg-IFN $\alpha$ dosing 			X															
PK sample collection 	731, Peg-IFN $\alpha$		X		X	X		X	X	X	X					X	X	
	ETV		X		X	X		X	X	X	X	X 				X	X	
HBcAb (IgM) 	X																	

Abbreviations: Ab = antibody; 731 = ABI-H0731; AE = adverse event; AFP = alpha fetoprotein; ALT = alanine aminotransferase; AST = aspartate aminotransferase; ECG = electrocardiogram; FSH = follicle-stimulating hormone; HAV = hepatitis A virus; HBcrAg = hepatitis B core-related antigen; HBeAb = HBeAg antibody; HBeAg = hepatitis B “e” antigen; HBsAb = HBsAg antibody; HBsAg = hepatitis B surface antigen; HBV = hepatitis B virus; HCV = hepatitis C virus; HDV = hepatitis D virus; HEV = hepatitis E virus; IgM = immunoglobulin M; INR = international normalized ratio; IRT = Interactive Response Technology; NA = not applicable; PK = pharmacokinetic; pgRNA = pregenomic RNA; T4=thyroxine; TSH = thyroid-stimulating hormone; ULN = upper limit of normal; Wk(s) = week(s).

 The assessments that need to be performed prior to the first dose of study drugs on Day 1 are listed in [Section 7.3](#).

 Study visits occur every 4 weeks between Weeks 24 and 60.

 Subjects who discontinue treatment before Week 24 (731 or Peg-IFN $\alpha$ ) or Week 48 (731) should immediately undergo the assessments listed for the Premature Termination Visit and then continue the scheduled follow-up assessments. ETV administration may be continued at the discretion of the Investigator.

 Any subjects with alanine aminotransferase (ALT) elevation should return to the clinic for an Unscheduled Visit. The minimum assessments to be completed when managing ALT elevations are noted in [Section 9.4](#).

 Liver staging is to be performed to determine lack of cirrhosis or advanced liver disease as required by inclusion criteria and should be performed by liver biopsy (within 1 year of Screening), by fasting FibroScan (within 3 months of Screening) or other Sponsor-approved hepatic imaging method within 6 months of Screening, and again at Weeks 24 and 48.

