#### **3.6.2. Definition of Study Phase**

The following phases will be defined: Randomized Treatment Phase and Overall Treatment Phase are on treatment; and the Follow-up Phase is off treatment.

- Randomized Treatment Phase: from first dose date through Week 24 visit (or premature termination visit if before Week 24)
- Overall Treatment Phase: from first dose date through Week 48 visit (or premature termination visit if before Week 48)
- Follow-up Phase: after Week 48 visit (or premature termination visit) through end of study

End of study will be when the subject completes the last visit of the follow-up period or is considered “lost to follow-up,” whichever is later.

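### The protocol does not say what happens to 731 when only Peg-IFN is stopped: its routing rules lead to ETV-only follow-up, its design section gives every subject 731+ETV from Week 24, and only Groups 2 and 3 are exposed to the conflict.

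*Combined protocol and SAP*

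**What the plan says.** **Trigger.** Section 7.10.1 lets a subject who tolerates treatment poorly stop 731 or Peg-IFN. The routing sentence then begins "Subjects who prematurely discontinue treatment (731 or Peg-IFN" and sends these subjects to the PT Visit and on to the Section 7.7 follow-up. The only drug it mentions as continuing is ETV: "Entecavir may be continued at the discretion of the Investigator". Appendix 1 footnote 3 repeats the trigger: "Subjects who discontinue treatment before Week 24 (731 or Peg-IFN" and so on, with 731 alone named for stops before Week 48.

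**Destination.** Section 7.7: "All subjects, including those who prematurely discontinue treatment or complete treatment per protocol will enter a 12-week follow-up period". It adds "Subjects will remain on ETV during the follow-up period", and ETV is the only drug in its list of procedures.

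**Design rule.** Section 4.1: "All subjects will receive 731+ETV from Week 24 through Week 48 and then ETV alone from Week 48 through Week 60". The synopsis and SAP 1.2 say the same. Section 4.3 is narrower: it places the 731+ETV period after the assigned treatment has been completed.

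**SAP.** Section 3.6.2 ends both on-treatment phases at the PT Visit if that comes early ("Overall Treatment Phase: from first dose date through Week 48 visit (or premature termination visit if before Week 48") and calls the Follow-up Phase off treatment. Section 3.6.3 starts the follow-up day count on the day after that visit. Sections 4.1 and 7.1.6 tabulate discontinuation of VBR, ETV and Peg-IFN separately.

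**The concern.** Premature treatment discontinuation is a component of the primary endpoint. Group 1 receives no Peg-IFN, so only Groups 2 and 3 contain subjects who can stop Peg-IFN alone. If that stop also ends 731 (Group 2) or prevents its Week 24 start (Group 3), part of any between-group difference in 731 discontinuation, and part of the missing Week 24–48 data, comes from the rule and not from tolerance of 731.

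If a site instead keeps the subject on 731+ETV, the SAP's phase definition puts by-visit data collected on VBR into off-treatment tables. Sites could follow either course in good faith, and the two courses give different data.

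**Working it through.** **Text check**

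1. The trigger is met by stopping either drug. Before Week 24, Group 3 takes no 731, so for that group it can only mean Peg-IFN.
2. The destination is a 12-week follow-up on ETV. Counting from the PT Visit, as SAP 3.6.3 does, a stop at Week 8 ends follow-up at 8 + 12 = Week 20, before 731 is due to start. A stop at Week 12 or later has the subject on ETV-only follow-up at Week 24.
3. Section 4.1 gives all subjects 731+ETV from Week 24, with no exception. For Group 3, steps 2 and 3 cannot both be followed unless Section 4.3's narrower wording governs.
4. Section 7.10.1 is also loose about *or*. For declining hepatic function it stops 731 *or* Peg-IFN, whereas Section 9.4 stops both. Its pregnancy paragraph says 731 *and* Peg-IFN. A site cannot tell from the conjunction whether a Peg-IFN stop carries 731 with it.

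**Arithmetic on the literal reading**

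Planned 731 tablets: 3 × 168 = 504 over 24 weeks and 3 × 336 = 1008 over 48 weeks, matching SAP 4.2.2.1.

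Planned 731 weeks lost if Peg-IFN alone stops at Week w:
- Group 2: 48 − w, that is 44 (w = 4), 40 (w = 8), 36 (w = 12), 28 (w = 20). At w = 8 the share is 40/48 = 83%.
- Group 3: all 24 weeks (504 tablets), whatever w is.
- Group 1: not reachable.

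Subjects affected: 60/3 = 20 per group, so each is 1/20 = 5% of a group. The documents give no Peg-IFN stop rate. Assuming 5–15%: 20 × 0.05 = 1 to 20 × 0.15 = 3 in each of Groups 2 and 3. The chance of at least one case among the 40 is 1 − 0.95^40 = 87% at 5% and 1 − 0.90^40 = 98.5% at 10%.

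**If 731 is continued (Peg-IFN stopped at Week 8, PT Visit on study day 56)**

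Follow-up Day 1 is study day 57, so follow-up day = study day − 56. In Table 3-6 the FU-Week 12 window opens at follow-up day 71, which is study day 127, or 127/7 = 18.1 weeks, and it has no upper bound.

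| Scheduled visit | Study day | Follow-up day | Assigned to |
|---|---|---|---|
| Week 12 | 84 | 28 | FU-Week 4 |
| Week 16 | 112 | 56 | FU-Week 8 |
| Week 20 | 140 | 84 | FU-Week 12 |
| Week 24 to last visit | 168 onward | 112 onward | FU-Week 12 |

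SAP 3.6.5 keeps the latest virology record in a window, so all virology from about Week 18 collapses into one FU-Week 12 value. For laboratory values and vital signs it keeps the record nearest the nominal day, here Week 20. The subject also leaves the Week 12–48 on-treatment summaries and the ANCOVA in SAP 6.1.2, which uses observed data only.

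**What the PT Visit does not cut**

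VBR exposure runs from first to last VBR dose (SAP 4.2.1, with dates from 3.6.3). TEAEs and treatment-emergent laboratory grades for the Overall Treatment Phase run to the last dose of any study drug plus 28 days (SAP 7.1.5.1, 7.1.6, 7.2.1.1).

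**The case against.** The strongest reply is that there is no contradiction: Section 4.1 describes the planned course and Section 7.10.1 the exception for those who leave it. Section 4.3 fits the literal routing, and footnote 3's distinction between stops before Week 24 and before Week 48 looks deliberate. This has force, and it is why the documents cannot be said to settle the matter either way. It does not remove the gap, because nothing states the status of 731 after a Peg-IFN-only stop.

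Three stronger readings are tempting, and the documents do not support them.

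- *A reader might infer that the protocol orders 731 to stop when Peg-IFN stops.* No sentence says so. The loss of 731 comes only from following 7.10.1 into 7.7.
- *A reader might infer that any interferon intolerance has this effect.* Sections 6.2.3 and 8.6 allow dose reduction, and Section 9.4 allows interruption and re-introduction. Only permanent discontinuation is routed this way. Where Section 9.4 directs a Peg-IFN stop for persistent ALT elevation or declining hepatic function, it also directs a 731 stop, so those cases are not created by the routing.
- *A reader might infer that up to 40 weeks of VBR exposure would be labelled off treatment.* That fails for exposure, TEAEs and treatment-emergent laboratory grades, which use dose dates. It holds only for by-visit data, and only if 731 is continued.

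It is also fair to say that separate per-drug tables are needed in any case, since planned durations differ; that SAP 4.1 already reports reasons for not completing each drug; that no formal inference is planned; and that treatment ended early in July 2022, so a protocol clarification cannot change how subjects were treated. These points limit the damage. They do not tell a reader of the disposition table which VBR stops followed only from a Peg-IFN stop. SAP 4.1 also has no category for a Group 3 subject who never started VBR.

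**Conclusion.** The point stands as an unresolved conflict with an asymmetric effect on the groups. On the literal reading, 731 discontinuation and missing Week 24–48 data in Groups 2 and 3 partly reflect the routing rule. On the other reading, by-visit virology, laboratory and vital-sign data collected on VBR are filed as off treatment.

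The likely size is 1–3 of about 20 subjects in each of Groups 2 and 3, and none in Group 1. This rests on an assumed 5–15% rate of permanent Peg-IFN-only stops. The weeks lost are measured against the planned 48 weeks; early termination of the study will have shortened them for some subjects. The matter deserves correction because it touches a component of the primary endpoint and the SAP part can be mended with data already collected. It does not undermine the exposure or adverse event summaries.

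**What to change.** 1. **Protocol.** Reconcile Sections 4.1, 4.3, 7.7, 7.10.1 and 9.4 and Appendix 1 footnote 3 on the status of 731 and the visit schedule after a Peg-IFN-only stop. Which clinical rule applies is the sponsor's decision. With treatment over, this mainly means recording in the report which rule sites followed.
2. **SAP phase rule.** For any subject with VBR doses after a PT Visit triggered by a Peg-IFN-only stop, do not end the on-treatment phase at that visit. End it at the Week 24 or Week 48 visit, or at the visit that follows the last VBR dose if that is earlier. Keep the PT Visit samples on treatment. Move follow-up Study Day 1 and FU-Baseline (SAP 3.6.3, 3.6.4, Tables 3-6 and 3-7) to the same anchor. Simply ending the phase at the last dose date in SAP 3.6.2 would not do: it would drop PT Visit samples taken after that dose and leave the follow-up anchors at the PT Visit.
3. **SAP disposition table (4.1).** Report VBR stops or non-starts that follow only from a Peg-IFN stop separately from VBR stops for other reasons.

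The cost is a few lines of SAP text and a little more programming; the dose and visit dates are already collected. The SAP changes belong before database lock; SAP Section 1 requires anything made after the SAP is final to be documented in the synoptic report.
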